#### **Analysis plan:**

1. A baseline table (Table 1) will describe overall study cohort characteristics by hematoma status.
2. Hematoma characteristics will be summarized at the patient level and also at the scan level (Table 2 and Table 3).
3. A 2x2 table of CT and InfraScanner results. Sensitivity, specificity, false positive value, false negative value, and their 95% confidence intervals will be calculated at patient level using the contingency table and reported. Repeat the analysis at scan level.
4. 2x2 tables of CT and InfraScanner results by quadrant. Corresponding counts and test characteristics will be calculated for each quadrant (frontal, temporal, parietal, and occipital). Repeat the analysis at scan level.
5. 2x2 tables of CT and InfraScanner results for hematomas within the detection limit. Corresponding counts and test characteristics will be calculated for hematomas within the detection limit (blood volume > 3.5 cc and distance from cranium < 2.5 cm). Repeat the analysis at scan level.

6. 2x2 tables of CT and InfraScanner results by types of hematoma. Corresponding counts and test characteristics will be calculated for each type of hematoma (SDH, EDH, etc.). Repeat the analysis at scan level.
7. 2x2 tables of CT and InfraScanner results by types of hematoma for those within the detection limit. Corresponding counts and test characteristics will be calculated for each type of hematoma (SDH, EDH, etc.) for those within the detection limit (blood volume > 3.5 cc and distance from cranium < 2.5 cm). Repeat the analysis at scan level.
8. Minimum blood volume detected as positive by InfraScanner 2000 will be reported.
9. Distributions of Blood Volumes and Difference in Optical Density ( $\Delta OD$ ) will be plotted for patients with hematoma.
10. InfraScanner results for special cases will be reported. Special cases include: patients who died, or had surgeries (craniectomy or craniotomy), or had ventricular effacement or midline shift.
11. Logistic regression model will be fit to assess the association between InfraScanner result and potential confounders that include patient age, sex, hair length, hair thickness, hair color, skin color, scalp laceration, scalp fracture, and scalp hematoma. Odds ratios with 95% CI will be reported.

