In industrialized nations, this is a trivial requirement, as CT scans are used ubiquitously to definitively diagnose EPH and SDH, readily and reliably triaging patients to surgical versus medical management. With 97% sensitivity, 98% specificity, 97% positive predictive value, 95% negative predictive value, and 96% accuracy in diagnosing Intracranial hematomas, CT scanning is exquisitely effective at identifying or ruling out acute extra-axial, intracranial bleeds in patients who sustain head trauma, making a gold standard in acutely assessing traumatic brain injury (TBI) (2). As a result, head CT has become commonplace, if not universal in assessing head trauma in industrialized countries, where virtually every hospital has one, if not a dozen scanners. In less than 10 minutes, a CT scan can noninvasively prove or reject acute intracranial bleeding. They

provide immediate insight into 1.) Whether there is in fact an intracranial bleed; 2.) In the case of a bleed, where below the cranium it has occurred and 3.) When done serially, gauge evolution, resolution, or stability of a bleed. This is invaluable information that directly impacts survival, as failure to perform a craniotomy in a patient with a rapidly expanding intracranial hematoma can swiftly lead to irreversible brain damage or even death. Moreover, performing such a surgery in the wrong location or in a patient who does not have a bleed amenable to surgical intervention can contribute extensive morbidity, exacerbating a patient's already tenuous mortality.

In less developed countries, CT scanners are often nonexistent. When they are present, they are extremely meager in number, peppered across treacherous geography, with scant transportation and emergency infrastructure. Even when accessible, they are commonly decommissioned due to a broken part, and are extremely cost prohibitive, with a single scan often costing the equivalent to multiple months' income for the populations who need them most. As a consequence, in the settings where TBI pervades and brain imaging is most critical to survival, obtainment of such imaging is often unachievable.

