10. Device Description/Mechanism: The following description is adapted from the InfraScanner White Paper (20): All biological tissue is, to differing extent, permeable to electromagnetic radiation of different frequencies and intensities. This can also be considered permeability to photons of different energy levels. This permeability to electromagnetic energy is the basis of all imaging based on transmission/scattering characteristics such x-ray, Computed Tomography, and near-infrared, NIR, imaging. From the principles of spectroscopy, it is also known that different molecules absorb different wavelengths of electromagnetic radiation (which is synonymously referred to as light at shorter wavelengths). Similarly, tissue scatters radiation to different degrees. The Infrascanner is concerned with NIR imaging of the hemoglobin molecules. From any light source, photons follow a characteristic path through the target tissue back to a detector on the same approximate plane as the source. While the light is severely attenuated due to the scattering and absorption process, it is nonetheless encoded with the spectroscopic signatures of the molecules encountered en route to the detector (Image C).

The principle used in identifying intracranial hematomas with the Infrascanner is that extravascular blood absorbs NIR light more than intravascular blood. This is because there is a greater (usually 10-fold) concentration of hemoglobin in an acute hematoma than in normal brain tissue where blood is contained within vessels. The Infrascanner compares left and right side of the brain in four different areas. The absorbance of NIR light is greater (and therefore the reflected light less) on the side of the brain containing a hematoma, than on the uninjured side. With specified wavelength ranges, optical light source(s) or emitter(s) and a photodetector are placed at a distance, which allows proper NIRS absorption measurements in a desired volume of tissue. The wavelength of 805nm is sensitive only to blood volume, not to oxygen saturation in the blood (Image D).

The Infrascanner is placed successively in the left and right frontal (F), temporal (T), parietal (P), and occipital (O) areas of the head and the absorbance of light is recorded. Specifically the placement is as follows:

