**Variables:**

1. Age: continuous
2. Sex: male/female
3. Skin color: white/light brown/dark brown/black/yellow
4. Hair thickness: bald/thin/medium/thick/MPB
5. Hair color: NA/white/grey/blond/light brown/dark brown/black/red
6. Hair length: bald/0-1 inch/1-3 inches/3-6 inches/>6 inches
7. Scalp hematoma present: Y/N, if yes, Y/N at 8 different locations (left/right frontal/temporal/parietal/occipital)
8. Scalp laceration present: Y/N, if yes, Y/N at 8 different locations (left/right frontal/temporal/parietal/occipital)
9. Scalp fracture present: Y/N, if yes, Y/N at 8 different locations (left/right frontal/temporal/parietal/occipital)

10. Positive infrascan: Y/N
11. Positive CT: Y/N, if yes, Y/N at 8 different locations (left/right frontal/temporal/parietal/occipital)
12. Ventricular effacement: Y/N
13. Midline shift: Y/N
14. CT blood location: Y/N, if yes, Y/N at 8 different locations (left/right frontal/temporal/parietal/occipital)
15. CT blood size: in cubic centimeters (cc) at 8 different locations (left/right frontal/temporal/parietal/occipital)
16. Distance-from-cranium: TBD

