**Table Shells:**

**Table 1: Study Population Characteristics**

	Hematoma present on CT N=	Hematoma not present on CT N=	Total N=	p-value
Gender Female Male				
Age N Mean (SD) Median Q1, Q2				
Skin Color				
Hair Color				
Hair Thickness				
Hair Length				
Mechanism of Injury Fall from elevation MVC Etc.				
Mortality				
GCS N Mean (SD) Median Q1, Q2				
Blood volume Left frontal Right frontal Etc. (?)				
Loss of Consciousness Yes No				
Location Frontal Temporal Occipital Parietal				
Hematoma Type SDH EDH Etc.				

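### The SAP's location tables ignore side, so a device positive on the side opposite the CT hematoma, in the same area, counts as a true positive

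*SAP*

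**What the plan says.** Analysis plan item 4 of the SAP calls for "2x2 tables of CT and InfraScanner results by quadrant" and continues: "Corresponding counts and test characteristics will be calculated for each quadrant (frontal, temporal, parietal, and occipital". The location row of the Table 1 shell is likewise unsided: "Location Frontal Temporal Occipital Parietal".

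The CT data are finer than that. SAP Variables item 11 reads "Positive CT: Y/N, if yes, Y/N at 8 different locations (left/right frontal/temporal/parietal/occipital", item 14 reads "CT blood location: Y/N, if yes, Y/N at 8 different locations", and item 15 records blood size at the same eight sites. Scalp hematoma, laceration and fracture (items 7 to 9) are also recorded by side and area. The one InfraScanner entry in that list, item 10, is "Positive infrascan: Y/N", with neither area nor side.

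Protocol section 10 describes the measurement: "The Infrascanner compares left and right side of the brain in four different areas". It defines ΔOD as a contrast within each left-right pair and says that the readout shows which region is bleeding.

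The SAP's definition of sensitivity concerns detection only. It sets no condition that the device's location agree with CT.

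**The concern.** Side is part of what this device measures: each reading is a difference between the two halves of the head. A table by area that drops side discards that part of the result. It cannot tell a right frontal bleed flagged on the right from one flagged on the left.

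Protocol section 2 says that a bleed must be both confirmed and located before surgery is pursued. In describing the value of CT, it names "performing such a surgery in the wrong location" as a source of harm. Aim 2 then uses this study's findings to judge whether a later trial, with the device used on its own, is feasible. Item 4 is the only planned table from which a reader could learn whether the device points to the right place, and as specified it cannot show wrong-side readings.

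**Working it through.** **Plan figures.** Item 4 states no figure of its own. The protocol's precision target concerns head-level sensitivity and is checked here only for scale: 1.645 × √(0.5 × 0.5 / 68) = 0.0997 (stated 0.099), and 68 / 0.13 = 523.1 (stated 523). The concern does not depend on either.

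**Step 1: classify one case.** Suppose that CT shows a single right frontal hematoma.

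| Device reading | Item 4, device result held by area | Item 4, if the head-level Y/N fills every table | Area and side must match |
|---|---|---|---|
| Right frontal | True positive | True positive in frontal, false positive in the other three | True positive |
| Left frontal | True positive | True positive in frontal, false positive in the other three | Wrong side |
| Temporal, either side | Miss in frontal, false positive in temporal | True positive in frontal, false positive in the other three | Wrong area |
| None | Miss | Miss | Miss |

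The second row is the finding: a wrong-side positive is a hit in item 4 however the device result is held. The third row is a hit only if the head-level Y/N is used.

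**Step 2: size of the side effect.** Let s be the sensitivity that the unsided table reports and w the share of those positives on the wrong side. Side-correct sensitivity is s × (1 − w). The documents do not give w. For illustration only, take s = 0.88, the figure quoted for the earlier device in hematomas above 3.5 cc and less than 2.5 cm deep, and assume values of w:

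- w = 0.05: 0.88 × 0.95 = 0.836
- w = 0.10: 0.88 × 0.90 = 0.792
- w = 0.20: 0.88 × 0.80 = 0.704

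The unsided table shows 0.88 in all three cases. If w = 0, the two agree.

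**Step 3: the head-level case, which is conditional.** Assume 500 patients, 13% prevalence (65 with hematoma, 435 without), one-area hematomas spread evenly, head-level sensitivity 0.88 and specificity 0.91. Each area then has 65 / 4 = 16.25 hematomas, with 48.75 elsewhere. If the single Y/N filled each table, per-area specificity would be (435 × 0.91 + 48.75 × 0.12) / 483.75 = 401.7 / 483.75 = 0.83. With results by area and false positives independent across the four pairs (assumed), it would be 0.91^(1/4) = 0.977.

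The gain in sensitivity in this case is small. A spurious positive in one of the other three areas has probability 1 − 0.91^0.75 = 0.068, so an area-correct sensitivity of 0.88 would be reported as 0.88 + 0.12 × 0.068 = 0.888, and 0.50 as 0.50 + 0.50 × 0.068 = 0.534. This case would therefore hurt the device on specificity more than it flatters it on sensitivity.

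**The case against.** The strongest reply is that item 4 was never meant as a localisation endpoint. The primary and secondary objectives concern detection. Location appears only in an exploratory objective in protocol section 13, as a factor that may affect test characteristics. Four area tables also fit the device, which gives one contrast per pair. This stands as to weight: the gap is in an exploratory table. It does not remove the gap, because no other planned table addresses side and the SAP has no matching rule.

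Three stronger readings are tempting, and the documents do not support them.

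- A reader might infer that positives in the wrong area also count as correct, since the listed device variable is a single Y/N. But item 4 speaks of "2x2 tables of CT and InfraScanner results by quadrant", which implies device results by area, and the protocol says that the device supplies them. The variable list is also visibly incomplete: it omits ΔOD (used in item 9) and hematoma type (items 6 and 7). The source of the area-level device result is an open question, not a stated error.
- A reader might infer that this study's results will themselves decide who is a candidate for craniotomy. Aim 2 only informs whether a later trial is feasible; candidacy belongs to that trial.
- A reader might take the illustrative values as an estimate of bias. The wrong-side share is assumed, and 0.88 comes from an earlier device and a restricted set of hematomas.

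A fair practical objection is that strict matching at eight sites would build in misses, because one contrast per pair cannot flag both sides of a bilateral hematoma. This stands, and the fix must handle it.

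**Conclusion.** The concern holds for side. As written, item 4 credits a same-area, wrong-side positive as a true positive, and nothing elsewhere in the plan corrects this. Per-area sensitivity can be overstated relative to side-correct detection by the factor 1 / (1 − w). The documents give no basis for w, so the amount is unknown and could be nil.

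For area, the conclusion is conditional: only if the head-level Y/N were used to fill the area tables would wrong-area positives become hits, and per-area specificity would then fall.

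The primary head-level sensitivity and specificity do not depend on this. It is a correction that should be made to an exploratory analysis that bears on Aim 2.

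**What to change.** 1. Keep the four area-pair tables. Add to the variable list a device result for each pair, with its side and signed ΔOD. Fix the sign by a left-right convention, since the protocol's formula is written in terms of the normal and hematoma sides.
2. Define a side-correct true positive as a device positive that matches CT in both area and side. Report it beside the unsided count.
3. Report the numbers of wrong-side and wrong-area positives, and one side-matched table pooled over areas.
4. State a rule for bilateral and multi-site hematomas: for example, classify them separately, or count either side as a match.
5. Repeat at scan level, as item 4 already provides.

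The cost is SAP wording, some programming and thin cells. With about 65 hematoma patients (13% of 500) in single areas spread evenly, each area has about 16, and the 90% half-width at p = 0.5 is 1.645 × √(0.25 / 16.25) = 0.20. The pooled table gives 1.645 × √(0.25 / 65) = 0.10, which is why it is needed.

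The fix depends on the sponsor confirming that sided, per-pair readings were stored for the 581 measurements. If only the head-level Y/N was kept, side agreement cannot be recovered by rewording the SAP, and the report should say that localisation was not assessed.

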In resource-limited settings, techniques such as ultrasonic measurement of the optic nerve sheaths and latency of the pupillary reflex have been used to infer increased intracranial pressure. However, these techniques are notably crude. They provide no insight into the location or etiology of what is causing the presumed increase in pressure, typically indicate an ICP >30 but are poor at correlatively quantifying ICPs as they grow emergently high, and in the case of optic nerve sheath diameter specifically, take up to a day to manifest. Hence, while these modalities can corroborate that a particular patient has increased ICP, these techniques are inadequate in determining which patients stand to benefit from surgery, and for those who could, in informing the surgical approach that could save such patient's lives.

In 1997, the first ever handheld device that could definitively detect the presence and location of epidural and subdural hematomas was introduced (3). Initially named the Runman, the device was intended to detect intracranial hematomas in remote and military settings to triage which casualties should be airlifted to medical centers equipped to offer neurosurgery. After numerous iterations, the InfraScanner 1000™ was introduced in the mid 2000's. In 2010, the pivotal five-site double-blinded clinical trial was published, and ultimately led to FDA clearance of the InfraScanner 1000™. In the study, the Infrascanner 1000™ measurements were compared to CT scans of 365 patients, 96 of which were hematoma cases of various sizes, depths and locations. The study demonstrated high sensitivity (88%) in detecting hematomas > 3.5cc in volume and < 2.5 cm from the surface of the brain, and a specificity of 91%. Since then there have been numerous studies that have replicated these results and have substantiated that it is a capable tool for pre-hospital diagnosis of intracranial hematomas (3-13).

While these results are extremely promising, the InfraScanner devices' utility has only been examined through the lens of pre-hospital decision-making. The sensitivity and specificity of the InfraScanner 2000™, introduced last year, has not been as exhaustively interrogated.

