- 13. Statistical Considerations:** Objectives: The primary objective of this study is to estimate the test characteristics (sensitivity, specificity, and the false positive and false negative rates) of the portable NIR-based device (InfraScanner 2000™) in the identification of any size hematoma among patients hospitalized at DUH who have sustained or who are suspected to have sustained head trauma and have consequently received a brain CT scan(s). The results of the CT scan(s) will serve as the gold standard. The sensitivity, specificity, and the false positive and

false negative rates will be estimated at the patient level and at the scan level. Approximately 90% of patients are expected to have more than one CT scan.

A secondary objective is to estimate the test characteristics of the InfraScanner 2000™ in identification of hematomas within its detection limits (volume >3.5 mL and depth <2.5 cm) compared to CT scan results as the gold standard.

Exploratory objectives include:

1. Examining the impact of factors such as hematoma type, location, and patient age on test characteristics of the InfraScanner 2000™
2. Determining the minimum resolution detectable by the InfraScanner 2000™
3. Estimating Receiver Operating Characteristic (ROC) curves with patient and scan as the units of analysis (21).

Study Design:

a) Eligibility:

Any patient who presents to DUH with suspected head trauma and receives a brain CT scan will be considered for this study. Based on previously reported data, we expect that SDH or EDH will be present in approximately 20% of patients overall.

b) Standard of comparison:

All patients entered onto the trial will undergo at least one cranial scanning using the InfraScanner 2000™ within 30 minutes of CT. Patients will be scanned using the InfraScanner 2000™ within 30 minutes of each subsequent CT. Patients will know the results of the CT but not the InfraScanner 2000™. The standard for comparison will be determined as follows. A CT result that is positive for hematoma will be considered a true positive and a CT result that is negative for hematoma will be considered a true negative. In cases where the results of the CT are negative for hematoma and the results of the InfraScanner 2000™ are positive consideration of further follow-up will be given on a case-by-case basis.

Definitions of Sensitivity, Specificity, False Positive, False Negative

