### **Statistical Analysis:**

#### **Definitions of the statistics of interest:**

Let A+ denote the event that the test is positive for hematoma and B+ denote the event that a hematoma is present. Sensitivity,  $P(A+/B+)$ , will be defined for each patient (scan) as the probability that a true hematoma as determined by CT scan will be detected (14). Similarly, let A- denote the event that the test is negative for hematoma and B- denote the event that a hematoma is not present. Specificity,  $P(A-/B-)$ , will be defined as the probability of being negative for hematoma on the InfraScanner 2000™ scan within 30 minutes of CT given the patient has no hematoma present.

The false positive rate will be defined as  $PF+ = P(B-/A+) = P(A+/B-)[1-P(B+)]/P(A+)$ . Similarly, the false negative rate will be defined as  $PF- = P(B+/A-) = [1-P(A+/B+)]P(B+)/[1-P(A+)]$ . Estimates for the false positive and false negative rates will be provided for a range of values for the prevalence of hematomas.

1. Estimation of test characteristics with 90% confidence at the patient level using SAS 9.4;
2. Estimate test characteristics at the scan level (treat each measurement as independent sample) and 95% confidence intervals will be computed as a secondary analysis.
3. Estimating Receiver Operating Characteristic (ROC) curves with patient and scan as the units of analysis with 95% confidence interval.
4. Fit a logistics regression of correct and incorrect detection from InfraScanner, adjusting for age, gender, skin color, hair color, hair thickness, hair length, scalp hematoma, scalp laceration, scalp fracture, ventricular effacement and midline shift.

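### The only SAP analysis that returns a minimum for the exploratory minimum-resolution objective is the smallest bleed that scanned positive; detected and missed counts by CT volume band should sit beside it

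*SAP*

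**What the plan says.** Protocol section 13 lists, as exploratory objective 2, "Determining the minimum resolution detectable by the InfraScanner 2000". It does not say what resolution means or how it is to be estimated.

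The SAP analyses that could bear on it are these:

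- Analysis plan item 8: "Minimum blood volume detected as positive by InfraScanner 2000 will be reported". No interval, detection probability or depth condition is attached, and the item does not call the figure a detection limit.
- Item 3: the overall CT by InfraScanner 2x2 table.
- Item 5: "Corresponding counts and test characteristics will be calculated for hematomas within the detection limit", the limit being preset at more than 3.5 cc and less than 2.5 cm.
- Item 7: "2x2 tables of CT and InfraScanner results by types of hematoma for those within the detection limit", with the same limit.
- Item 9: "Distributions of Blood Volumes and Difference in Optical Density" will be plotted for patients with hematoma.
- Statistical Analysis item 3: ROC curves by patient and by scan, with no mention of volume.
- Statistical Analysis item 4: "Fit a logistics regression of correct and incorrect detection from InfraScanner". Neither volume nor depth is in its covariate list.
- Analysis plan item 11: "Logistic regression model will be fit to assess the association between InfraScanner result and potential confounders". Again neither volume nor depth is listed.

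The Variables list already holds the device result (item 10) and CT blood size in cc at 8 locations (item 15). Distance from cranium (item 16) is still to be determined.

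**The concern.** A reader looking for the answer to objective 2 will find one number in cc. The same kind of number could come from a size the device nearly always misses, with one lucky positive, or from a size it usually finds. Item 8 has no denominator, so it cannot tell these apart.

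This has some weight because the protocol's Aim 2 is to inform a future trial of stand-alone use where CT is not available. There, how often bleeds of a given size are missed matters more than the smallest one ever found. The stake is limited to the reading of one exploratory objective.

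**Working it through.** **1. What follows from the definition alone.** Item 8 is the minimum of CT volume over device-positive bleeds. One case sets it. A missed bleed of any size leaves it unchanged. Adding bleeds to the set can lower it or leave it, never raise it. No assumption is needed.

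**2. The plan's own figures, for scale.** Item 8 states no number to reproduce. The revised sample size gives 68/0.13 = 523 patients, as stated. The half-width at 90% is 1.645 × sqrt(0.25/68) = 0.0997 (stated 0.099), and with 455 negatives 1.645 × sqrt(0.25/455) = 0.0386 (stated 0.038). The SAP's final sample is 500 patients. At the 13% prevalence in the protocol's Administrative Summary this is 0.13 × 500 = 65 hematoma patients.

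**3. Illustration on assumed inputs.** The documents give no volume distribution and no detection curve. I assumed 65 bleeds, log-normal volumes with median 5, 10 or 20 cc and log-SD 1.2, and no chance positives, with three curves:

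- A: p = expit(2 × ln(V/3.5)), which is 50% at 3.5 cc rising to 100%
- B: 0.88 × A
- C: 0 up to 3.5 cc, 0.88 above it

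The 0.88 echoes the earlier model: "The study demonstrated high sensitivity (88%) in detecting hematomas > 3.5cc in volume".

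Results for median volumes 5 / 10 / 20 cc:

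| Curve | Median item 8 figure (cc) | Mean true detection at that volume | Mean missed bleeds at least that large |
|---|---|---|---|
| A | 1.5 / 2.0 / 2.8 | 17 / 25 / 39% | 17 / 10 / 5 |
| B | 1.6 / 2.1 / 2.9 | 16 / 24 / 35% | 21 / 16 / 12 |
| C | 3.6 / 3.7 / 3.9 | 88% | 5 / 6 / 7 |

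With log-SD 0.8 to 1.6, and the slope halved or doubled for A and B, the median figure runs from 0.9 to 4.3 cc.

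**4. Chance positives.** The earlier model's 91% specificity suggests, as an assumption, a 9% background rate. The chance that at least one of k undetectable bleeds scans positive is 1 − 0.91^k: 38% for k = 5 and 61% for k = 10. Under curve C this lowers the median item 8 figure from about 3.6 to 3.9 cc to about 1.2 to 3.6 cc.

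**5. What volume bands would show.** Average sensitivity up to 3.5, 3.5 to 10, and above 10 cc:

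- A: 22–29%, 72–75%, 96–98%
- B: 19–25%, 64–66%, 84–86%
- C: 0%, 88%, 88% (a 9% background would lift the 0% to 9%)

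Expected patients per band are 25/22/18, 12/20/33 and 5/14/47 for median volumes of 5, 10 and 20 cc.

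**6. Precision of bands.** Three equal bands hold 65/3, about 21 patients each. The worst-case half-width is 1.645 × sqrt(0.25/21) = 0.18 at 90% and 1.96 × sqrt(0.25/21) = 0.21 at 95%. Curves A and B differ by only about 3 to 12 points per band, so one study could not tell them apart. The contrast between a gradual fall-off and a sharp threshold is larger (22–29% against 0% in the lowest band), provided that band is not nearly empty.

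**The case against.** The objective is undefined, and the smallest bleed detected is one literal reading of it. Item 8 promises only to report that number and draws no inference from it. This stands: no stated rule is broken, and item 8 can stay as description.

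Other items cover part of the ground. Subtracting item 5 from item 3 gives detected and missed bleeds outside the preset limit, which would already help to tell a hard threshold at that limit from a gradual curve. Item 9 covers all patients with hematoma, so missed bleeds are in the plot. This also stands, with two limits. The group outside the limit mixes small bleeds with deep ones, and there is only one cut. The SAP does not say that the plot is joint or marks misses.

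The cc values rest on assumed inputs. True, but the argument in step 1 does not use them. Adding chance positives changes the values and makes item 8 harder to interpret, not easier.

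Bands at this sample size are coarse. True, and step 6 gives the limit.

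A reader might infer more: that the SAP passes item 8 off as a detection limit, that its figure is bound to fall far below the true limit, or that no planned analysis shows missed bleeds. The documents do not support these. Item 8 makes no such claim. Under a hard threshold without chance positives the figure settles near the threshold. Items 3, 5, 7 and 9 all include missed bleeds.

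**Conclusion.** The point holds as an optional improvement. Item 8 is the only planned analysis that returns a minimum, and by construction it ignores misses and cannot rise. No planned analysis gives detection by volume beyond the single preset cut. That conclusion rests on the text alone.

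How far the figure could mislead is unknown, because it depends on the volume distribution, the detection curve and the chance-positive rate, none of which the documents give. On the assumptions above, true detection at the reported size averages anywhere from 16% to 88%, and item 8 read alone does not show which applies. The objective is exploratory, and no primary or secondary estimate changes.

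**What to change.** Keep item 8 as a descriptive figure and add beside it: *Among CT-positive patients, detected and missed counts and sensitivity with confidence intervals will be reported by CT blood-volume band, with band cuts (one at 3.5 cc) fixed before device results are examined by volume.* The timing clause matters because the SAP already states a final sample, so the cuts may be chosen after enrolment.

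Two definitions are needed:

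- Say whether a patient's volume is the sum or the largest of the 8 locations.
- Choose each patient's scan by CT, for example the first CT-positive scan with a paired InfraScan. The SAP's Data Management rule picks the scan by the device result and names none for a patient the device never flags. At most 581 − 500 = 81 patients have more than one measurement, but for them the band counts may differ from the patient-level table in item 3, and a footnote should say so.

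A logistic curve on log volume, or a volume for 50% detection, is left to the trial statistician and is not part of this fix.

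The cost is one SAP item with these definitions, on variables already listed. Depth can be added once it is defined. The downsides are wide intervals and a lowest band that may be thin: about 5 of 65 patients if the median volume were 20 cc. The bands can show a sharp threshold against a gradual fall-off, but not small differences between detection curves.
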